### 5.7.2 Statistical Analyses

Analyses will be conducted by the lead biostatistician in collaboration with resources from the Coordinating Site Committee (see above).

**Demographics:** All unit level and patient level categorical demographic information will be summarized on table 1 as proportions and frequencies. We will output all continuous data using mean plus standard deviation or median plus range.

**C. difficile acquisition Rate:** Acquisition rates will be obtained from each unit and comparisons for differences between control and intervention units using a chi-squared test. We will conduct a crude and adjusted linear and logistic regression model to determine predictors of C.diff acquisition in patients. Additionally, we will model the incidence of C.diff acquisition for intervention and control patients using Poisson regression models and to determine the gloving impact.

**CDI Infection Rate:** For unit-level data, we will compare changes in CDI infection rates between the intervention and control units using the chi-squares test or Fisher's exact test with post-hoc pairwise comparisons. For patient-level data, infection rates will be modelled for specific time periods (during 3, 6, 9 and 12 months; or every 3 months of the study period [up to 24 months]) using incidence split modeling to determine the point of highest infection within each unit, with appropriate covariate adjustment. We will use the Royston's trend test to conduct a time-trend analysis for CDI infection rates for specific time periods (during 3, 6, 9 and 12 months; or every 3 months of the study period).

**Other HAI Rates:** All other rates between intervention and control units will be compared using chi-squared test or Fisher's exact test, with post-hoc pairwise comparisons. All incidence and risk analysis will be conducted using Poisson regression models with covariate adjustment. For specific time periods (during 3, 6, 9 and 12 months; or every 3 months of the study period), we will use incidence split modeling to determine the point of highest infection within each unit, with appropriate covariate adjustment. We will use the Royston's trend test to conduct a time-trend analysis on the monthly HAI (CAUTI and CLABSI).

**Length of Stay:** A weighted two-sample and paired t-test will be used to compare mean length of stay between the intervention and control units.

**30-Day Mortality:** Using patient level data, we will conduct a 30-day survival analysis to determine the hazard of mortality for control and intervention units using a cox proportional hazards model with Kaplan Meier curves. Within each unit, a risk analysis will be conducted to

determine the predictors of 30-day mortality. Additionally, we will examine survival percentages at specific periods of the intervention period (i.e. 3, 6, 9 and 12 months; or every 3 months of the intervention period) using life tables and log-rank tests to determine at which points mortality was highest for each unit.

*Other clinical outcomes:* Rates of toxic megacolon and colectomy will be compared between intervention and control units using chi-squared test or Fisher's exact test, with post-hoc pairwise comparisons. All incidence and risk analysis will be conducted using Poisson regression models with covariate adjustment. For specific time periods (during 3, 6, 9 and 12 months), we will use incidence split model to determine the point of highest infection within each unit, with appropriate covariate adjustment. We will use the Royston's trend test to conduct a time-trend analysis on the monthly outcomes.

*Intervention Fidelity:* We will calculate the compliance rates for both the intervention and control units and compare them using a chi-squared test. We will conduct a univariate logistical regression model to determine the odds of compliance with respect to additional unit characteristics such as number of beds and location. Monthly compliance will be modeled using a time series graphing technique with trend analysis estimates.

*Isolation Days of Care:* Monthly aggregate data of isolation patients will be collected from infection control at participating sites which are collected as standard of care and we will estimate the days of care by multiplying this number by the average length of stay for the participating unit. We will make comparisons between the intervention and control groups using the analysis of variance (ANOVA).

*Healthcare Worker Experience:* After verification of transcription accuracy, team members will use VA-approved software to facilitate data organization, coding, and retrieval. Qualitative content analysis will inductively generate codes and categories rather than using an a priori coding scheme or researcher-generated coding scheme. Line by line coding will be conducted to identify codes or statements of meaning (level I coding). Codes that emerge will be grouped into larger categories (level II, coding for themes).

*Patient Experience:* After verification of transcription accuracy, team members will use VA-approved software to facilitate data organization, coding, and retrieval. Qualitative content analysis will inductively generate codes and categories rather than using an a priori coding scheme or researcher-generated coding scheme. Line by line coding will be conducted to identify codes or statements of meaning (level I coding). Codes that emerge will be grouped into larger categories (level II, coding for themes).

*Cost:* Descriptive statistics will be used to describe nursing time frequencies and percentages. Paired t-tests will be used to compare average provider time for donning and doffing between the intervention and control units. We will use Royston's trend test to examine the monthly costs of supplies over time.

*Provider-Patient Contact Surveys:* We will compare the differences in reported contact between the intervention and control units.

*Missing data:* We will resolve all missing data using a case-wise analysis technique or multiple imputation solution.

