## **5.1 Study Procedures**

### **5.2 Study Design**

#### **5.2.1 Experimental Design**

We will conduct this study using a pragmatic stratified-cluster randomized trial (CRT) in ten inpatient VA hospital units (acute medical, medical/surgical, or surgical inpatient acute care units). Hospital units will be randomly assigned in a 1:1 ratio: 5 units will be randomized to enact universal gloving practices (intervention) and 5 units will continue standard of care (control).

Due to resource and personnel feasibility, randomization will be stratified by location to allow for the selection of one intervention and one control unit at each site.

A 6-12-month pre-intervention period will be used to conduct preliminary work at sites including training research assistants, identifying current practices, finalizing monitoring and observation plans. Each participating unit will collect data for up to 24 months – a 24-month intervention period. During the intervention period, we will collect data on a monthly basis, including C. difficile acquisition and infection rates, other infections (CLABSI, CAUTI, MRSA), mortality, length of stay, and intervention fidelity (hand hygiene compliance and barrier precaution compliance; glove use for all patients and glove plus gown use for patients in CP isolation). These unit-level data will be obtained from aggregate reports prepared by the infection control department at each site from data they have entered into the VA Inpatient Evaluation Center (IPEC) data management system and/or from VA administrative records. Patient-level data on relevant clinical characteristics such as comorbidities, prior treatments and healthcare usage, and outcomes such as HAIs will be obtained from VA administrative records for patients who consent to stool specimen collections. We will conduct interviews/focus groups with healthcare workers throughout the intervention period and individual interviews with patients throughout the intervention period. These interviews and focus groups will explore healthcare workers' and patients' experiences with the intervention. We will also conduct patient and healthcare worker survey on provider-patient contact using a Likert scale to assess the amount of contact patients have with their healthcare workers in both the intervention and control groups.

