It is not possible to carry out the study using written individual informed consent. In this study, we are performing a cluster randomized trial. Cluster randomized trials such as these most often are granted waived consent due to the inability to carry out the research without waiver of consent. As is the case for many infection control or behavioral interventions, this intervention cannot be studied using a traditional patient-level randomization because: a) the intervention is difficult if not nearly impossible to randomize to individual patients in the unit and not other patients; b) there are group-level variables in patient units (patient-specific variables and healthcare worker-specific variables) that make the CRT the most valid study design; and c) bacteria transmission does not occur on the individual level but on a group level within a patient unit. An example of a group level variable is colonization pressure. Colonization pressure, defined as the percent of patients in a given patient unit with an infectious agent such as an antibiotic-resistant organism (MRSA), affects the probability of other patients acquiring the bacteria and developing an infection (primary and secondary outcomes of the study). Since wearing gloves and gowns to care for a particular patient (e.g., patient A) would protect that patient from acquiring an infection, but would also prevent other patients (e.g., patient B, patient C, patient D) in the same unit from acquiring bacteria from patient A. Another reason is that if the study was randomized to individual patients, it is likely that healthcare workers would be influenced by the intervention of wearing gloves and gowns and potentially being more adherent to other infection control practices. A patient-level randomized trial is inadequate to study interventions that reduce transmission of infections. CRT is the preferred design in many infectious disease and infection control studies when the investigator is worried about contamination of intervention to control patients.

(1) The research involves no more than minimal risk to the participant. Use of barrier contact precautions (gloving plus gowning) is currently the standard of care for patients with certain communicable diseases including antibiotic-resistant organisms (e.g., MRSA), so the expansion of universal gloving for care of all patients (intervention) does not present additional risk to healthcare workers or patients.

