### **5.8 Data Analysis**

#### **5.7.1 Sample Size Determination**

Initial power calculation determined that 10 patient units are necessary to detect a 36% relative reduction (6.2%) in acquisition of *C. difficile* in the intervention vs. no reduction in the control group based on a presumed rate of 9.7 acquisitions per 1,000 patient days; recent literature report an average *C difficile* acquisition rate of 9.7 per 1,000 patient-days and expected reduction of *C. difficile* acquisition of 36%. Each arm of the study will require 9,879 patient days of care. On average, it is estimated that each patient unit will have a 25-bed capacity with an estimated 100 admissions per month and 5-day length of stay. We will plan to enroll 10 units, 5 for each arm. These power calculations will be revised based on actual baseline-period data. The statistical power calculation was conducted using G\*Power. We have incorporated an intracluster coefficient of 0.40 for this study.

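### Ten units are randomised in five site pairs, but the between-arm tests for acquisition, CDI, other HAIs, mortality and fidelity carry no between-unit variance, and neither acquisition test is named as primary

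*Combined protocol and SAP*

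**What the plan says.** Section 5.2.1 describes a stratified cluster randomised trial of ten units, five per arm, in which "randomization will be stratified by location to allow for the selection of one intervention and one control unit at each site". Section 5.4 justifies the cluster design on the ground that "bacteria transmission does not occur on the individual level but on a group level within a patient unit". The sample-size section (5.7.1) states "Each arm of the study will require 9,879 patient days of care" and "We have incorporated an intracluster coefficient of 0.40 for this study".

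The between-arm analyses in section 5.7.2 are:

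- **Acquisition:** "Acquisition rates will be obtained from each unit and comparisons for differences between control and intervention units using a chi-squared test". Incidence is also modelled "using Poisson regression models and to determine the gloving impact". The linear and logistic models in the same paragraph are for predictors and are not at issue.
- **CDI:** chi-squared or Fisher's exact test.
- **Other HAIs:** "All other rates between intervention and control units will be compared using chi-squared test" or Fisher's exact test, plus covariate-adjusted Poisson models. Toxic megacolon and colectomy are treated the same way.
- **30-day mortality:** analysed "using a cox proportional hazards model with Kaplan Meier curves".
- **Fidelity:** chi-squared test on compliance.

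Paired t-tests are named for length of stay and for donning and doffing time, without saying what is paired. No paired method is named for the outcomes listed above.

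**The concern.** The unit that was randomised is the ward. With one ward per arm at each site, the arm comparison rests on five paired differences, which leaves 4 degrees of freedom for a paired analysis. Chi-squared, Fisher, Poisson and Cox methods, applied without a cluster adjustment, build their standard errors from patients or patient-days. They treat any chance difference between wards as evidence about gloving. The error grows with follow-up, because the assumed sampling error shrinks while the ward-to-ward component does not.

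The risk is a false claim that universal gloving works, or that it harms. The Abstract says a positive result would change how CDI is prevented in healthcare. Section 5.7 (Safety Monitoring) also acts on a significant fall in hand hygiene compliance, and the fidelity test would over-call such falls. Having two acquisition tests with neither named as primary adds a choice that could be made after the data are seen.

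Leaving out the site stratum does not itself inflate type I error. Site belongs in the analysis to match the design and recover precision.

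**Working it through.** **Inputs from the documents.** 9.7 acquisitions per 1,000 patient-days, a 36% reduction (to 6.2), 9,879 patient-days per arm, five units per arm, 100 admissions per unit per month, 5-day stay, up to 24 months, and 200 hand hygiene opportunities per unit per month.

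**Assumed.** Two-sided 5% and 80% power (neither is stated), and between-unit CVs within site of 0.1 to 0.4 (none is given).

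**1. The plan's own figure.** The ordinary two-proportion formula with independent patient-days is

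n = [1.96·√(2·0.00795·0.99205) + 0.842·√(0.0097·0.9903 + 0.0062·0.9938)]² / 0.0035² ≈ 10,106 per arm.

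This is within 2.3% of 9,879; an arcsine version gives 9,983. At 9,879 the power is 79.1%. So the stated size is reproduced with no design effect, although section 5.7.1 says an ICC was incorporated. The ICC does not enter any analysis standard error either.

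**2. Variance left out of the acquisition test.** With Poisson counts of mean μ per unit and between-unit CV k, the variance of the arm difference is inflated by 1 + μk². The actual size of a nominal 5% test is about 2·[1 − Φ(1.96/√(1 + μk²))].

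- Stated size: 9,879/5 = 1,976 patient-days per unit, so μ = 1,976 × 0.0097 = 19.2.
- Ceiling: 100 × 5 × 24 = 12,000 per unit (60,000 per arm), so μ = 116.4. This counts every bed-day, and real exposure will be lower because acquisition needs consent and paired samples.

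| Unit CV | Inflation, 9,879 | Type I error | Inflation, 60,000 | Type I error |
|---|---|---|---|---|
| 0.1 | 1.19 | 7.3% | 2.16 | 18% |
| 0.2 | 1.77 | 14% | 5.66 | 41% |
| 0.3 | 2.73 | 23% | 11.5 | 56% |
| 0.4 | 4.07 | 33% | 19.6 | 66% |

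A gamma-Poisson simulation with 40,000 runs per setting gives the same values to within about a percentage point. The unadjusted Poisson test is within 0.5 points of the chi-squared test. At the stated size its nominal 95% interval covers 93%, 86%, 76% and 67%. With site variation only (site CV 0.2 or 0.4, unit CV 0), chi-squared type I error is 5.0% to 5.2%.

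**3. A cluster-level test.** A paired t-test on the five within-site differences in log(count + 0.5), with 4 df, has type I error between 4.6% and 5.2% in the same simulations. Its power for a 36% reduction is:

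| Unit CV | 9,879 per arm | 60,000 per arm |
|---|---|---|
| 0 | 54% | 99.8% |
| 0.1 | 48% | 94% |
| 0.2 | 37% | 65% |
| 0.3 | 27% | 38% |
| 0.4 | 20% | 25% |

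**4. Fidelity (hand hygiene).** 200 × 24 = 4,800 observations per unit. With assumed 70% compliance and a unit SD of 2 percentage points, the inflation is 1 + 4,799 × 0.0004/0.21 = 10.1, which gives type I error of about 54% (53% by simulation). For contact-precaution compliance, 12 × 24 = 288 contacts per unit, the inflation is 1.55 and type I error about 11%. Universal gloving compliance is observed only in intervention units, so it has no between-arm test.

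**5. The ICC of 0.40.** Its scale is not stated. Read as a patient-level ICC with 9,879/5/5 = 395 patients per unit, the design effect is 1 + 394 × 0.40 ≈ 159, and simulated type I error is 85%. At a risk of 0.0097 × 5 = 4.85% it would imply a between-unit CV of √(0.40 × 0.9515/0.0485) ≈ 2.8, far outside the range above. This figure is illustrative and nothing below depends on it.

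**The case against.** **The text may imply a cluster analysis.** Rates are obtained per unit, and some models are covariate-adjusted. But chi-squared has no between-unit variance term, fixed covariates do not supply one, and no unit effect is named. This does not rescue the plan.

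**The size depends on assumed CVs.** This stands. At CV 0.1 and the stated size, type I error is only about 7%. The 56% to 66% results need CV 0.3 to 0.4 and the 60,000 ceiling. The direction of the error does not depend on the CV.

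**Fidelity is uneven.** This also stands. The 53% applies to hand hygiene only, and Aim 3 treats fidelity as descriptive.

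**The power loss depends on the method.** An unpaired t-test on the ten log unit rates (8 df) also keeps type I error near or below 5%. With no site variation its power at the stated size is 67%, 60%, 46%, 33% and 24% for CV 0 to 0.4. With site CV 0.2 that advantage disappears: at unit CV 0.2 it has about 34% against 37% paired at the stated size, and 54% against 64% at 60,000. It also ignores the stratification.

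**Only acquisition and fidelity were quantified.** True. For CDI, other HAIs and mortality the fault is the same in kind, but the documents give no rates from which to size it.

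**Two unranked tests matter little.** They have nearly equal type I error, so the lack of a named primary analysis is the smaller part of the point.

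**Conclusion.** The concern holds and must be fixed. The plan randomises wards in site pairs but names between-arm tests whose standard errors omit ward-to-ward variation. This is an error in the methods as written, beyond a lack of detail. For acquisition, assumed within-site CVs of 0.1 to 0.4 turn a nominal 5% test into one of about 7% to 33% at 9,879 patient-days per arm, and 18% to 66% at the 24-month ceiling. The hand hygiene comparison has type I error of about 53% under an assumed 2-point unit SD and 70% compliance. The qualitative conclusion needs only some variation between wards within a site. Confidence is high on the fault and moderate on its size, because the documents give no between-unit CV.

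**What to change.** 1. Name one primary acquisition analysis that respects unit randomisation and site pairing. Either of these would serve:
   - a t-test and confidence interval on the five within-site differences in log unit rate (4 df), with a stated rule for zero counts such as adding 0.5; or
   - a Poisson or negative-binomial mixed model with a patient-day offset, site as stratum, unit as random effect and small-sample degrees of freedom. A simpler version, overdispersed Poisson with site terms and 4 df, had type I error of 4.8% to 5.4%. The full mixed model was not simulated and should be checked before it is adopted.
2. Stop using unadjusted chi-squared, Fisher, Poisson and Cox methods as between-arm tests.
3. Apply the same principle to CDI, other HAIs, 30-day mortality and the fidelity measures observed in both arms. Report toxic megacolon and colectomy descriptively, or with a method suited to sparse counts: at an assumed 0.3 events per unit, the log-rate t-test is undefined in 7.8% of simulated trials and has type I error of 1.0%. Check expected counts for the other HAIs before choosing a log-rate method.
4. Restate power for the chosen analysis when the revision promised in section 5.7.1 is made, with the assumed between-unit CV and the scale of the ICC given.

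The predictor models may stay as written.

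**Cost.** SAP wording, wider intervals (critical value 2.78 in place of 1.96, plus between-unit variance) and lower stated power, as tabulated above. From CV 0.2 upward, the site-paired test stays below 80% power even at 60,000 patient-days per arm, so longer follow-up in ten units does not restore it. The sponsor should be told this before the analysis is fixed.

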## 5.6 Study Evaluations

### Patient-level data

**C. difficile Acquisition:** In both the intervention and control groups, we will obtain one swab or stool sample upon admission and one swab or stool sample upon discharge to test for the presence of *C. difficile*. This outcome data will be collected on an individual patient level, but de-identified prior to reporting. These test results will not be available to healthcare workers or patients at participating sites. Acquisition will be defined as a patient who has an initial test (via stool or perirectal swab) upon unit admission that is negative for *C. difficile* and a subsequent discharge test within the same unit that is positive for *C. difficile*.

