### Specimen collection

Research staff and/or clinical staff in both the intervention and control arms of the study will implement a standard protocol for obtaining stool or perirectal swab (depending on patient preference) samples for *C. difficile* test using standardized clinical methodology. Samples will be collected within 72 hours of patient admission and within 72 hours of anticipated discharge of all patients in participating units. *C. difficile* testing via stool sample will be obtained by using a toilet hat to collect stool and storing a sample of the stool in a sterile contained. *C. difficile* testing via perirectal swab sample will be obtained by swabbing the perianal area (a swab from the anal verge, without rectal insertion) in a circular motion, ideally until visible stool is noted on swab. The swab samples will be obtained in a private room or the privacy curtain will be drawn in semi-private rooms to protect patient privacy. The discharge sample may be collected within 72 hours prior to estimated discharge date or, if the patient is transferred to another unit within the participating facility, within 48 hours after discharge from the unit. Samples collected by research staff will be labeled with unique identifier. Samples collected by clinical staff or patient self-collected samples will be labeled in the unit by clinical staff with standard clinical pre-printed patient labels and collected on site by Research Assistants who will relabel specimens with unique identifiers. These collected samples will be refrigerated according to procedures defined by laboratory staff to ensure sample quality and then ship in batches to the Madison VA research laboratory.

The specimens will be shipped to a central microbiological research laboratory at the Wm. S.

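### The acquisition model has no unit or site term and does not pre-specify imported carriage, so a chance imbalance over five ward pairs can shift the gloving estimate behind too narrow an interval

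*Combined protocol and SAP*

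**What the plan says.** Section 5.4 (Informed Consent Procedures), in arguing for cluster randomisation, states "An example of a group level variable is colonization pressure". It adds that this pressure "affects the probability of other patients acquiring the bacteria and developing an infection", and identifies those events as the study's primary and secondary outcomes.

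Section 5.6 provides the raw material for a measure of imported carriage in both arms: "we will obtain one swab or stool sample upon admission and one swab or stool sample upon discharge". On timing it says "Samples will be collected within 72 hours of patient admission and within 72 hours of anticipated discharge of all patients in participating units". Sections 5.4 and 5.4.1 require verbal consent and a signed HIPAA authorization for specimens, so in practice only consenting patients are sampled. The admission result has one stated use: acquisition means a negative admission test followed by a positive discharge test on the same unit.

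Section 5.2.1 sets up five pairs: "randomization will be stratified by location to allow for the selection of one intervention and one control unit at each site".

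Section 5.7.2 compares acquisition between arms by a chi-squared test and then says "we will model the incidence of C.diff acquisition for intervention and control patients using Poisson regression models and to determine the gloving impact". The same paragraph has adjusted models, but for another purpose and without listed covariates: "We will conduct a crude and adjusted linear and logistic regression model to determine predictors of C.diff acquisition in patients". Covariate adjustment of Poisson models is written down for other healthcare-associated infections and for other clinical outcomes, not for acquisition. Neither colonization pressure nor admission prevalence appears in the analysis section.

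**The concern.** The plan gives a unit-level cause of the primary outcome as a reason for its design and collects specimens from which the imported part can be estimated. It then does not say that the model for the gloving effect will use that information. The hypothesis is about asymptomatic carriers as a reservoir, so the number of carriers a ward admits is an obvious reason for two wards to differ whatever their glove policy.

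Ten units in five pairs is too few to rely on chance balance. If the gloving wards happen to admit fewer carriers, the rate ratio falls without any gloving effect. A Poisson model with no unit or site term treats every acquisition as independent, so its interval reflects event counts only. The estimate can move by a large amount while the reported uncertainty stays small. A false positive would support a practice change that the plan hopes will be nationwide; an imbalance the other way would hide a real effect.

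**Working it through.** **1. The plan's own figure.** Section 5.7.1 asks for 9,879 patient-days per arm, at 9.7 acquisitions per 1,000 patient-days and a 36% reduction, that is 6.2 per 1,000. It states neither alpha nor power; two-sided 0.05 and 80% are assumed here. With p̄ = (0.0097 + 0.0062)/2 = 0.00795:

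n = [1.96·√(2·0.00795·0.99205) + 0.8416·√(0.0097·0.9903 + 0.0062·0.9938)]² / 0.0035² = (0.2462 + 0.1057)² / 0.00001225 ≈ 10,106.

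This is 2.3% above 9,879; the arcsine version gives 9,984 (1.1% above). Other alpha and power pairs also come close, so the match is not unique. All of these formulas treat patient-days as independent. The stated intracluster coefficient of 0.40 does not appear to enter the figure.

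**2. Planned volume.** 100 admissions × 5 days = 500 patient-days per unit-month. Over 24 months and 5 units that is 500 × 24 × 5 = 60,000 per arm.

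**3. Shift from chance imbalance in imported carriage alone.** Assume acquisition is proportional to imported carriage and log carriage varies between wards of a site with standard deviation s. The SE of the mean log ratio over five pairs is s·√(2/5), and the null 95% range is exp(±1.96·SE).

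| s | SE | Null range of the rate ratio |
|---|---|---|
| 0.2 | 0.126 | 0.78 to 1.28 |
| 0.3 | 0.190 | 0.69 to 1.45 |
| 0.5 | 0.316 | 0.54 to 1.86 |
| 0.3, half dependence | 0.095 | 0.83 to 1.20 |

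The target is 0.64 (log −0.446).

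**4. Why the Poisson interval is too narrow.** Expected events per arm under the null are 9,879 × 0.0097 = 95.8, or 60,000 × 0.0097 = 582. The model's SE is √(2/95.8) = 0.144, or √(2/582) = 0.059. With s = 0.3 and full dependence the true SD is √(0.144² + 0.190²) = 0.238, or √(0.059² + 0.190²) = 0.199. The interval's half-width is then 1.96 × 0.144/0.238 = 1.19 true SDs, or 1.96 × 0.059/0.199 = 0.58. The false-positive rate is about 24%, or about 56%, instead of 5%.

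**5. Simulation under no gloving effect.** 2,000 trials per scenario, five sites with one unit per arm. Assumed: 8% admission carriage, all admissions sampled, between-unit coefficient of variation (CV) of carriage 0.25 to 0.50, within-site correlation 0 to 0.5, dependence exponent 0.5 to 1. Cells show the percentage of trials with p < 0.05.

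| Patient-days per arm | CV, correlation, exponent | Poisson, arm only | Poisson, arm + admission carriage | Paired t by site, unadjusted |
|---|---|---|---|---|
| 9,879 | no carriage variation | 4.4 | 5.1 | 5.4 |
| 9,879 | 0.25, 0.5, 0.5 | 6.5 | 6.4 | 5.0 |
| 9,879 | 0.50, 0, 1 | 39.2 | 9.8 | 4.6 |
| 60,000 | no carriage variation | 5.6 | 5.7 | 5.2 |
| 60,000 | 0.25, 0.5, 0.5 | 15.3 | 6.2 | 5.1 |
| 60,000 | 0.50, 0, 1 | 70.9 | 11.6 | 5.1 |

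The mean log rate ratio stayed near 0 throughout (−0.007 to 0.012). In the CV 0.50 rows shown, 8.9% and 7.2% of null trials showed a reduction of 36% or more with the arm-only model; without carriage variation it was 0.2% or less. The covariate cut the SD of the log rate ratio in those rows from 0.341 to 0.194 and from 0.319 to 0.085.

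**6. When carriage is not the only source of unit variation.** Assume half dependence on carriage (s = 0.3), other unit variation of SD 0.3, 8% carriage, and 400 or 1,200 sampled admissions per unit. A Poisson model with site pair and half-yearly log carriage still rejects in 27% of null trials at 9,879 patient-days per arm and 59% at 60,000, against 29% and 63% without the covariate. A paired t-test stays near 5%. Adding the covariate to the paired analysis raises the SD from 0.26 to between 0.31 and 0.33 at 9,879. Where carriage is the sole driver, it lowers the SD from 0.20 to 0.10 at 60,000.

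**The case against.** The strongest reply is that this is mostly unmodelled clustering, seen through one of many unit-level factors. That largely stands: the unadjusted paired analysis held 4% to 6% in every scenario of step 5 without any carriage term, whereas the covariate without a unit term did not restore 5%. A reader might infer that adding admission carriage to the stated model cures the problem; steps 5 and 6 show otherwise. What the reply leaves open is the point estimate. A paired analysis reports honest uncertainty but does not remove the imbalance from the estimate.

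A reader might also infer that the estimate is biased, or that the plan rules adjustment out. Neither is supported. Randomisation makes the estimate right on average, and allocation within site removes carriage shared by a hospital's two wards. Section 5.7.2 is silent on covariates for this model; it does not exclude them. It would also be wrong to say that the imbalance widens the interval, because the interval as written ignores it.

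The covariate is imperfect too. Specimens may be taken up to 72 hours after admission, against an expected 5-day stay, so some early acquisitions on the unit will count as imported, and gloving could affect those. Only consenting patients are sampled. Section 5.4 defines colonization pressure as the percentage of patients on the unit carrying the agent, which is not the same as imported carriage. These points stand and limit what adjustment can achieve.

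**Conclusion.** The concern holds in a limited form. The model for the gloving effect has no unit or site term and does not pre-specify a unit-level driver that the plan itself names and approximately measures. A chance imbalance in imported carriage over five pairs can therefore move the one rate ratio observed, behind an interval too narrow to reflect it.

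The size rests on a between-ward SD, a dose-response and an admission prevalence that the documents do not give. Over the step 5 scenarios with carriage variation, the arm-only model rejects a true null in 6.5% to 39% of trials at 9,879 patient-days per arm and 15% to 71% at 60,000. The low ends apply when the two wards of a site are alike and acquisition depends weakly on carriage.

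The missing unit and site structure is the main defect. Pre-specifying admission carriage is an inexpensive secondary improvement: it helps when carriage drives the differences between wards and can cost precision when it does not. That trade-off makes it a supporting estimate, not the sole primary model.

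**What to change.** In section 5.7.2, under the acquisition rate:

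1. Estimate the gloving effect with an analysis that respects unit and site pair. Examples are a paired analysis of the five site log-rate differences, or a Poisson model with a unit random effect, site pair and small-sample inference.
2. Pre-specify a supporting estimate that adds one unit-level covariate to that analysis: the log share of sampled admissions positive on the admission specimen, by unit and period. Fix the period length and the handling of zero counts in advance.
3. Build the covariate from admission specimens only. Total prevalence on the unit is itself changed by gloving, and adjusting for it could remove part of the effect.
4. Report the estimate with and without the covariate, and state the two measurement limits (the 72-hour window and consenting patients only).

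No new data are needed. The main analysis will give a wider interval than the current model, because the current one is too narrow. In a five-pair analysis the supporting estimate leaves 3 residual degrees of freedom instead of 4 (critical t 3.18 instead of 2.78), may lose precision if carriage explains little, and is attenuated by measurement error in the share. Naming the covariate before the data are seen is what makes the adjusted result credible.
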